13.1 Risks

Potential Risks of Weight Loss Intervention: Rapid weight loss (loss of > 3 lb. per week for 3 or more weeks) may increase the risk of gallstones. Symptoms of gallstones include abdominal pain, nausea, vomiting, fever, and chills. Rate of weight loss will be monitored in all subjects to identify those at risk.

Potential Risks of the Medication: The following are the common side effects that have been reported with phentermine treatment (because the medication was approved in 1959, they do not have a defined frequency): high blood pressure, palpitations, elevated heart rate (tachycardia), dizziness, overstimulation, restlessness, insomnia, changes in mood (euphoria or dysphoria), changes in libido, tremor, headache, dry mouth, unpleasant taste, diarrhea, constipation, and other gastrointestinal disturbances.

Rare side effects that may be associated with taking phentermine include:

- **Acquired Valvular Heart Disease.** Cases of developing heart valve disease were reported in people taking phentermine in combination with fenfluramine. Fenfluramine appeared to be responsible for the valvular heart disease. It was removed from the market in 1997. Phentermine did not appear to contribute to valvular heart disease, but this possibility cannot be completely ruled out.
- **Primary Pulmonary Hypertension.** This condition is a rare, frequently deadly disease of the lungs. It was observed in persons who took the combination of phentermine and fenfluramine. Fenfluramine appeared to be responsible for this illness and was removed from the market. The possibility of an association between primary pulmonary hypertension and the use of phentermine alone cannot be ruled out. No cases of the disease have been reported with the long-term use of phentermine and topiramate, marketed as Qsymia.
- **Abuse Potential.** Phentermine is chemically and pharmacologically similar to amphetamines which have a high abuse potential. One study found no signs of drug craving, abuse, dependence, or amphetamine-like withdrawal upon abruptly ceasing the medication, even at doses higher than typically recommended and after treatment durations of up to 21 years.⁷¹ However, the possibility of abuse with phentermine should be considered in deciding whether to prescribe this medication. Individuals who have a history of drug abuse will not be eligible to participate.
- **Central Nervous System Effects.** Phentermine may impair physical and mental abilities. Caution should be taken when driving or operating machinery, or drinking alcohol. Individuals with an overactive thyroid (hyperthyroidism) will not be eligible for to take phentermine.
- **Glaucoma.** Phentermine may cause excessive dilation of the pupils which can worsen narrow angle glaucoma. Patients with a narrow angle glaucoma diagnosis will not be eligible to participate.
- **Drug Interactions.** Use of phentermine is contraindicated during or within 14 days following the administration of monoamine oxidase inhibitors (MAOIs) because of the risk of hypertensive crisis. The effect of co-administering phentermine with selective serotonin norepinephrine reuptake inhibitors (SNRIs) has not been investigated. Participants will be asked to inform the study physician or nurse practitioner immediately if they are prescribed one of these medications during the study period.

CONFIDENTIAL

29

- **Kidney Impairment.** Phentermine has not been studied in persons with kidney impairment. Persons with clinically significant kidney disease are not eligible for this study.
- **High Blood Pressure.** Phentermine may cause an increase in blood pressure. Individuals with a blood pressure is $\geq 140/90$ not be eligible to participate in this study. Individuals with a history of coronary heart disease, congestive heart failure, or other significant cardiovascular disease (see exclusions) also will not be eligible. We will monitor participants' blood pressure at every study visit.
- **Unforeseen risks.** Such risks include allergic reactions to medications. In addition, there may be other risks associated with phentermine that have not been identified. If additional risks are identified during the study, study subjects will be informed about these risks by the study team.
- **Reproductive risks.** The use of phentermine may pose risks to pregnancy and/or an unborn baby. Therefore, subjects are advised not to get pregnant while in the study. Women of child bearing potential will be required to follow a study-approved method of birth control while participating in the study. Adequate birth control in this study is the use of double barrier methods (condom with spermicide or diaphragm with spermicide), stable hormonal contraception, intrauterine device, abstinence, or tubal ligation. In addition, the study medication may have unknown risks to breast-fed babies. Therefore, study subjects are instructed not to breastfeed while taking the study drug.

Risks of the Assessment: Risks of drawing blood include pain, bruising at the puncture site, swelling, feeling faint or lightheaded, and, rarely, infection.

Confidentiality and Loss of Privacy: All efforts will be made to ensure that subject information obtained during the course of this study will be kept confidential. However, we cannot guarantee total privacy. Personal information may be given out if required by law.

13.1.1 Protections Against Risks.

Weight Loss Intervention: Subjects will be informed of all potential risks when providing consent before enrolling in the study. They will be able to withdraw from the study at any time. Risk of gallbladder disease will be minimized by limiting weight loss to no more than 3 lb. per week for 3 consecutive weeks. Subjects who exceed this limit will be advised to increase their calorie intake.

Study Medication: As in previous studies conducted at the Center, e.g., 58, 59, 79, 82, 112 we will make every attempt to minimize, assess, and manage the occurrence of any side effect or adverse event (AE) of the study medication. Subjects will be screened for medical conditions that would preclude the use of phentermine, and stringent exclusionary criteria will be employed to limit the possibility of AEs (see above). Subjects will be informed about the possibility of medication side effects, including symptoms of rare but serious conditions, during informed consent and prior to randomization to medication or placebo (for randomization-eligible subjects who lose $< 2\%$ after 4 weeks of BT). A list of the subject's current medications will be collected during the screening, and subjects will be asked to inform study staff before starting any new medication during the course of the study.

To reduce the likelihood of side effects, randomized subjects will be taught how to properly perform the subcutaneous injection of the study medication (phentermine or placebo), and the medication will be initiated at 0.6 mg/day and increased by 0.6 mg at weekly intervals until a dosage of 3.0 mg/day is achieved. Subjects who do not tolerate an increased dose during escalation will delay escalation by up to 7 days. Subjects will be instructed, if they miss a dose, to resume the once-daily regimen with the next scheduled dose and not to take an extra or higher dose. If they miss more than 3 days, they will be instructed to call the study medical staff who will re-initiate therapy at 0.6 mg/day to avoid gastrointestinal symptoms. Subjects will be taught how to properly store the medication and dispose of needles.

Randomized subjects will be asked to report any new symptoms to the research staff. In addition to assessment visits, randomized subjects will have a brief medical visit (10-15 minutes) with study staff (e.g., registered nurse) at week 2 (after initiation of the medication) and week 6 (after most subjects will have completed dose escalation) to monitor response to the medication. Side effects will be queried during every

study visit, and the study NP or physician will be available to assess the subject and evaluate and treat any adverse events. Subjects will be encouraged to contact study staff immediately should an AE occur between visits, and 24-hour contact information will be provided for study personnel and the study physician. If any AE requires treatment follow-up, subjects will be provided with appropriate referrals. For all non-study-related medical events, subjects will be referred to their own primary care provider.

During outcome assessments and brief medical visits, patients will be asked about their mood or any thoughts of harming themselves through administration of the Columbia-Suicide Severity Rating Scale. Additionally, online questionnaires assessing depressive symptoms will be checked within 24 hours of their completion for signs of severe depression, including suicidal ideation. (Participation in a weight loss program is not a risk factor for depression and typically results in improvements in mood.¹¹³) In the event of mental health events, subjects will be referred to the study's psychologist or psychiatrist for further evaluation to determine if clinical intervention is needed (i.e., referral to a mental health provider).

Subjects of childbearing potential will provide a urine pregnancy test during their initial assessment and again prior to randomization to a study medication and must agree in writing to use an approved method of contraception throughout the study. Approved methods include the use of double barrier methods (condom with spermicide or diaphragm with spermicide), stable hormonal contraception, intrauterine device, abstinence, or tubal ligation. Subjects will be asked to immediately notify the study team, discontinue the drug (if applicable), and consult with an obstetrician if they become pregnant during the study. Subjects who become pregnant will be withdrawn from the study medication and BT treatment. The study physician or NP will follow up with any such patients during pregnancy and after childbirth to assess adverse events.

Randomized subjects will have the option to stop taking study medication at any time. The PI or study physician may also withdraw a subject from the medication if medically appropriate. Stopping study medication will not preclude subjects' completion of the BT program (unless weight loss is contraindicated).

Confidentiality and Loss of Privacy: All applicable national and international guidelines, regulations, and Institutional Review Board (IRB) guidelines regarding subject privacy and confidentiality will be followed throughout the study. No identifying information will be included with stored research data, biological samples, clinical data, or reports of results. Penn network firewalls prevent unauthorized internal access to data, external access to data, and malicious intent to destroy data and systems. Controlled user access will ensure that only appropriate and authorized personnel are able to view, access, and modify study data. Data sent to the IRB, Investigational Drug Services, or the Data and Safety Monitoring Board will contain no identifying information, except as required when reporting AEs. Password-protected files linking subject names and ID numbers will only be accessible to the PI and research coordinator, and will be stored in a locked office. Publications will be based on analyses of de-identified data, and subject ID numbers will only be included if necessary to clarify an individual patient event. Patient privacy will be protected by conducting all assessments and treatment visits in closed examination rooms or offices, where only the patient and appropriate staff member are present. Subjects will not be video or audiotaped at any point during the study.

Biological Sample Storage: All samples and medication will kept in a secure refrigeration room accessible only to relevant study staff. Biological samples stored for later analysis will be labeled with the patient ID and relevant assessment code, and, after being centrifuged and separated, will be frozen at -80 °C.

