15. Narrow angle glaucoma
16. Presence or history of marked agitation
17. Current severe major depressive episode (BDI-II score ≥ 29), current active suicidal ideation, or history of suicide attempts within the past 5 years.
18. Any severity of thought or bipolar disorder, or bulimia nervosa.
19. Psychiatric hospitalization within the past 6 months
20. Self-reported alcohol or substance abuse within the past 6 months, including at-risk drinking (current consumption of ≥ 14 alcoholic drinks per week)
21. Past year history of drug abuse.
22. Use in the past 2 weeks of monoamine oxidase inhibitors.
23. Current use of serotonin-norepinephrine reuptake inhibitors (SNRIs; e.g., venlafaxine, duloxetine, desvenlafaxine, milnacipran, levomilnacipran).
24. Use in past 6 months of medications known to induce significant weight loss (e.g., prescription weight loss medications) or weight gain (e.g., chronic use of oral steroids, second generation antipsychotics)
25. Loss of $\geq 5\%$ of initial body weight within the past 6 months
26. History of (or plans for) bariatric surgery (e.g., roux en y gastric bypass, sleeve gastrectomy, gastric banding), endoscopic intragastric balloon, or aspire assist.
27. Inability to walk 5 blocks comfortably or engage in some other form of aerobic activity (e.g., swimming)
28. Known or suspected allergy to sympathomimetic amines or related products
29. The receipt of any investigational drug within 6 months prior to this trial
30. Previous participation in this trial (e.g., randomized and failed to participate)
31. Changes to any chronic medication (type or dosage) within the past 3 months.

32. Any serious or unstable medical or psychological condition that, in the opinion of the investigator, would compromise the patient's safety or successful participation in the study

Investigational Product (drug, biologic, device, etc.)	
For Drug, food, cosmetic, etc. include the dose, route of administration and dose regimen	Phentermine 15.0 mg/day, provided in capsule form. (Study medication will be initiated at 8.0 mg/day for the first 2 weeks and increased to 15.0 mg/day thereafter.)
Duration of administration (if applicable)	24 weeks
Reference therapy	Placebo for phentermine

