3.1 General Design

This is a two-phase study. Phase 1 will evaluate obesity-related behavioral and biological characteristics as potential mechanisms of non-response to BT. Phase 2 is a double-blind, placebo-controlled, RCT to test whether augmenting BT with weight loss medication improves 24-week weight loss, as compared to BT with placebo, in subjects identified as early non-responders to 4 weeks of individual behavioral weight control. Subjects will be a total of 150 adults, aged 21-70 years, with a body mass index (BMI) of 31 kg/m² or above (28 kg/m² with an obesity-related comorbidity). Subjects will attend a screening visit in which they will complete a behavioral evaluation with a psychologist and a medical history. In phase 1, eligible subjects will complete questionnaires and an in-person baseline assessment of obesity-related behavioral characteristics (satiety, hunger, RRV_{food}, and impulsivity), neuropeptides, and gastric emptying. Within 2 weeks of this assessment, they will begin an initial 4-week BT “run-in” delivered individually in 20-30 minute sessions. The primary goal of phase 1 will be to evaluate baseline postprandial satiety, postprandial change in GLP-1, and gastric emptying as predictors of early weight loss after 4 weeks of BT. We will also examine whether these variables predict categorization as an early non-responder to BT who loses < 2.0% of initial weight (vs. early responders who lose ≥ 2.0%; approximately 33% vs. 66% of the sample, respectively).

In phase 2, early non-responders (who lost < 2.0% during the BT run-in) will be randomly assigned to 24 weeks of: 1) BT plus placebo (BT+P); or 2) BT plus medication (BT+M; phentermine 15.0 mg). Both treatment groups will continue to attend 20-30 minute individual BT sessions, weekly for the first 12 weeks and every other week for the last 12 weeks (total of 18 visits). Both treatment groups will also take once daily study medication (placebo or phentermine 15.0 mg) for the duration of the intervention period (with titration between randomization and week 2). Early BT responders identified during the run-in will receive the same 24-week BT program, but will not receive study medication or be included in the randomized trial. The assessments administered at baseline – questionnaires, including behavioral testing, blood draws, and measurements of body weight – will be repeated at randomization (week 0) and at week 24.

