5.3 Medication and Placebo Interventions

In addition to attending BT sessions, non-responders will take a once daily study medication (phentermine or placebo) beginning at the randomization visit. The study medication will be provided in capsule form, and participants will be encouraged to take the medication in the morning upon awakening. Subjects will receive a 30-day supply of the study medication on each of 6 occasions. Phentermine will be provided as 8.0mg/d for the first 2 weeks to facilitate its acceptance to participants. The dose will be increased at week 2 to 15 mg/d (or further placebo) in all participants. Phentermine (or placebo) will be down-titrated (back to 8.0mg/d) or terminated in patients who report that they cannot tolerate the medication after a prolonged effort to do so. Down-titration will be managed in a blinded manner by Penn's Investigational Drug Service (IDS), in response to notification from the principal investigator (or study co-investigators) of patients' complaints of symptoms. (With IDS, we successfully used this titration method in prior randomized placebo-controlled trials of sibutramine for weight loss⁸² and of the addition for 12 weeks of phentermine or placebo to liraglutide 3.0 mg.⁸³) Participants in whom phentermine (or placebo) is terminated will continue to receive BT for the remainder of the 24-week treatment period.

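### Section 13.1.1 describes an injected regimen of 0.6 to 3.0 mg/day with a week 6 medical visit; the rest of the protocol describes capsules of 8.0 then 15 mg/day with that visit at week 4

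*Combined protocol and SAP*

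**What the plan says.** **Section 13.1.1 (Protections Against Risks, Study Medication).** On dose, this section states that "the medication will be initiated at 0.6 mg/day and increased by 0.6 mg at weekly intervals until a dosage of 3.0 mg/day is achieved". On route, it has randomised subjects "taught how to properly perform the subcutaneous injection of the study medication (phentermine or placebo"). The same paragraph adds "Subjects will be taught how to properly store the medication and dispose of needles". Escalation may be delayed by up to 7 days if an increased dose is not tolerated. A subject who misses more than 3 days is to call the medical staff, "who will re-initiate therapy at 0.6 mg/day to avoid gastrointestinal symptoms". Brief medical visits are set at week 2 and at "week 6 (after most subjects will have completed dose escalation").

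**The rest of the protocol.** The features are spread over several sections:

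- Study Summary: capsules; "Study medication will be initiated at 8.0 mg/day for the first 2 weeks and increased to 15.0 mg/day thereafter"; medical visits at weeks 2 and 4.
- Section 3.1: once-daily medication "for the duration of the intervention period (with titration between randomization and week 2").
- Sections 3.2 and 5.4: the drug service packages the medication in blinded capsules.
- Section 5.3: "The study medication will be provided in capsule form", with 8.0 mg/d for two weeks and 15 mg/d from week 2 in all participants. Subjects who cannot tolerate the drug are down-titrated to 8.0 mg/d or taken off it.
- Section 10.6: medical visits at week 2, after two weeks at 8.0 mg, and at week 4, after two weeks at 15.0 mg for most subjects.

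Nothing marks section 13.1.1 as superseded, and it is not part of an amendment log.

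**The concern.** Section 13.1.1 is where the ethics board reads how side effects of the study drug will be limited. The route and doses given there cannot be delivered with the capsules that the drug service supplies. The protection it describes is therefore not the regimen described elsewhere.

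Two practical points follow. First, 13.1.1 holds the only restart rule in the visible text, and its restart strength is absent from the capsule regimen, so staff cannot apply that part as written. Second, the week of the second medical visit is stated two ways. Section 13.1.1 also places the suicidality scale at the brief medical visits, so the timing of one administration is left open.

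**Working it through.** The plan gives no single figure to reproduce here. The check sets the texts side by side and works out what each schedule implies.

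| Feature | Section 13.1.1 | Elsewhere |
|---|---|---|
| Route | Subcutaneous injection, needles | Capsule (Summary, 3.2, 5.3, 5.4) |
| Starting dose | 0.6 mg/day | 8.0 mg/day (Summary, 5.3, 10.6) |
| Target dose | 3.0 mg/day | 15 mg/day (Summary, 3.1, 5.3, 10.6) |
| Escalation | +0.6 mg weekly | One increase at week 2 (Summary, 5.3) |
| Restart after more than 3 missed days | 0.6 mg/day | No rule in the visible text |
| Second medical visit | Week 6 | Week 4 (Summary, 10.6) |

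**Escalation.** In 13.1.1 the number of steps is (3.0 − 0.6)/0.6 = 4, giving 0.6, 1.2, 1.8, 2.4 and 3.0 mg/day. The target is reached at week 4, or at week 5 after one 7-day delay. In 5.3 there is one step, 8.0 to 15 mg/day, at week 2.

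**Overlap of doses.** The ranges are 0.6–3.0 and 8.0–15 mg/day. The gap is 8.0 − 3.0 = 5.0 mg/day, so no dose level is common to both.

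**Second medical visit.** The two statements are 6 − 4 = 2 weeks apart. Each fits its own schedule: in 13.1.1 the visit falls 6 − 4 = 2 weeks after the target dose is reached (1 week after one delay), and in 10.6 it falls 4 − 2 = 2 weeks after. The visit conflict thus follows from the regimen conflict and is not counted as a second, independent one. The week 6 vital signs listed in the Summary and 10.6 are a separate item and do not amount to a week 6 medical visit.

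**Suicidality scale.** This timing is derived. Only 13.1.1 ties the scale to the brief medical visits; the Summary and 10.6 do not mention it there. If the scale goes with the visit, one administration moves by the same 2 weeks. Those at screening (7.1), at the week 2 visit and at the outcome assessments (8.4, 13.1.1) are unaffected.

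**Handling of intolerance.** Section 13.1.1 allows a delay in escalation. Section 5.3 raises the dose in all participants at week 2 and provides for down-titration or termination later. Section 13.1.1 also lets the subject stop, or the principal investigator or study physician withdraw, the medication. These need alignment but are not counted as a direct contradiction.

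**Blood pressure (minor).** Section 13.1 promises a measurement at every study visit. The Summary lists specific weeks, and 10.6 limits them to in-person visits. What counts as a study visit is not defined in the visible text and Table 1 could not be seen, so only the mismatch in wording is noted.

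**The case against.** The strongest reply is that this is stray wording with little practical consequence. The drug service packages capsules and manages down-titration, no other visible section mentions injection or needles, and the ethics board has 5.3 and 10.6 in the same document. Subjects attend weekly behavioral sessions through week 12, side effects are asked about at every study visit, and vital signs are listed for both week 4 and week 6 (in-person visits only, in 10.6). Safety contact is therefore planned in both weeks under either text. Nor does the whole missed-dose passage fail: subjects can still call the medical staff after more than 3 missed days, and the instruction to resume at the next scheduled dose after a single miss does not depend on route or strength.

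Most of this stands, and it limits the consequence: only the restart strength fails, and the visit conflict does not leave subjects unobserved. It does not remove the contradiction. A reader may guess that a capsule is not injected, but cannot tell from the text which visit week applies or what restart instruction staff should follow. However the wording arose, it is operative text in the safety section.

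**Conclusion.** The concern holds. One regimen is described in two ways that disagree on route, starting dose, target dose and escalation and share no dose level, and the second medical visit differs by 2 weeks. This is an internal inconsistency that must be fixed, because 13.1.1 sets dosing, restart and visit rules for all randomised subjects (50 in 4.6 and 9.1; 60 in the Summary) that cannot be followed alongside 5.3 and 10.6.

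The restart rule reaches only subjects who miss more than 3 days, and the intolerance text only those who do not tolerate the drug; the documents give no expected number for either. The power inputs in 9.1 are stated for phentermine 15.0 mg and are not affected. The finding rests on the visible text alone. Table 1 could not be checked, but its content would not remove the conflict between the sections compared here.

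**What to change.** Reconcile 13.1 and 13.1.1 with the Summary, 3.1, 3.2, 5.3, 5.4 and 10.6, so that one description of each of these appears throughout:

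- route, doses and escalation;
- handling of intolerance, missed doses and restart;
- timing of the medical visits and of the suicidality scale;
- the blood-pressure schedule, including what applies at remote visits.

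Then check Table 1, the consent form and the staff instructions against it. Which text is right is a decision for the sponsor's clinicians, and no dose, route, restart rule or visit week is proposed here.

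The cost is a short protocol amendment and a consistency check. Design, sample size and analysis do not change.
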